5.5.3 Method of Assigning Subjects to Treatment Groups

All infants will be centrally randomized using a secure, password protected web-based randomization system within the RAVE™ DMS available 24 hours/7 days per week via any computer with high-speed internet access. Directions for the randomization system are presented in the MOP. Eligible infants will be assigned a unique randomization number that allocates them in a 1:1 ratio to receive inositol or placebo. To ensure balance between the treatment groups, randomization will be stratified by center and by 2 gestational age risk strata (<26 and 26-27 weeks).

Randomization will be performed at the overall study level. For regulatory analyses, the randomized study population will be administratively split within study center in a pre-determined manner to define the regulatory sub-study A and sub-Study B (see SAP).

5.5.4 Selection and Timing of Dose for Each Subject

Infants will receive either: 80 mg inositol/kg/day or placebo (80 mg glucose/kg/day), administered in divided doses every 12 hours (40 mg/kg/dose). Study drug will be administered daily and continued until the earliest of 34 completed weeks PMA, 10 weeks (70 days) chronologic age, or the time of discharge. Inositol or placebo will be administered IV until enteral feedings are established, at which time the same dose and formulation will be administered enterally every 12 hours. If an infant subsequently becomes ill and enteral feedings are discontinued, dosing will resume IV until they are able to sustain enteral feeds again (120ml/kg/day, or sooner if IV fluids have been discontinued).

Study drug doses will not be adjusted for estimated inositol enteral intake from formula or human milk.

If an infant is discharged from the participating center hospital (home or back-transfer), study drug will be stopped unless the infant is transferred to a center/site that is also participating in the INS-3 protocol (repeat consent may be needed).

5.5.4.1 Adjusting Dose for Growth

The per-kilogram doses of inositol and placebo will be based on the birth weight of the infant, until such time that the infant's weight exceeds the birth weight (usually 1-3 weeks). Thereafter, on a once-per-week basis, the daily dose will be recalculated for current weight based on the weight measured that week.

If an infant becomes too unstable to weigh, or in the event serious third space edema develops (as for instance may occur if an infant is septic), the clinically estimated 'dry weight' (weight preceding the event) of the infant should be used instead of current weight (which may differ by as much as double or more of the "dry weight"). This is the usual clinical practice in the NICU for calculating dosing for other drugs in these circumstances. This 'dry weight' is adjusted by the clinical team on a weekly basis allowing for underlying growth if good calories are being given. When the clinically evident edema has resolved, or the estimated "dry weight" is within 10% of the measured weight, the dose calculation will revert to being based on current weight.

5.5.4.2 Discontinuation of Dosing for Oliguria

Renal insufficiency represents a special case that sometimes occurs in premature infants. Because so much inositol is excreted in the urine in the initial weeks after birth, study drug administration will be discontinued if an infant becomes oliguric (urine output of 0.5 mL/kg/hour or less, over 24 hours), or if the serum creatinine rises to 1.8 mg/dL or higher during the study. If, however, an infant entered the study with an elevated creatinine due to maternal elevated creatinine (allowed up to 2.5 mg/dL) and the serum creatinine is falling, this would not meet the criteria for stopping drug.

If a recognized, reversible cause of oliguria is diagnosed (e.g., congestive heart failure from a PDA, status post indomethacin administration for PDA, sepsis with hypotension), and the infant fully recovers (urine output >1.0 mL/kg/hour over 24 hours for at least 3 days and creatinine <1.8 mg/dL and falling), study drug will be resumed at the previous dose. However, if the period of renal dysfunction lasts more than 14 days, study drug will not be resumed, even if the condition diagnosed is a recognized, reversible cause of oliguria. If a recognized cause of oliguria cannot be identified, even if the episode resolves, study drug will not be resumed.

5.5.5 Masking of Study Group (Blinding)

Inositol and placebo (dextrose/ glucose) are both clear, colorless, slightly sweet solutions that are identical in appearance and contain the same concentration of carbohydrate (50 mg/mL).

Each site's study-certified pharmacist will be responsible for tracking, dispensing, and documentation of study drug, as well as reporting directly to the Data Coordinating Center any protocol deviations/violations that would involve unmasking if other study personnel were to report them.

The site pharmacist will dispense study drug in unit dose delivery syringes in order to mask all clinicians, research personnel, and families to the investigational product administered. In the event of a serious adverse event that appears related to study drug, dosing may be stopped without unmasking. A MedWatch form will be completed and reported to NICHD, the Data Coordinating Center, and the local Institutional Review Board (IRB) per their procedures. The NICHD will determine if individual reporting to the FDA and AN is indicated. If events make it necessary, the pharmacy at each site will be able to unmask the study drug given to an individual infant; however, the pharmacist must contact the Center's Investigator, the overall study Principal Investigator, or the NICHD Program Scientist prior to releasing this information, and a protocol violation form will be completed. Contact information for these individuals is provided in the MOP.

5.5.6 Treatment Compliance

Each dose of study drug administered is to be documented including the date, time, actual dose of inositol/placebo received, route, and dosing weight. The Investigator or his/her designated and qualified representatives will administer study drug only to subjects enrolled in the study in accordance with the protocol. The study drug must not be used for reasons other than that described in the protocol.

5.5.7 Drug Accountability

Study drug will be shipped to each site's pharmacy. The study-certified pharmacist will verify that study drug supplies are received intact and in the correct amounts. It will be the responsibility of the site's study-certified pharmacist to maintain an accurate (running) inventory of all study drug dispensed and to perform and verify an overall accountability of the study drug throughout the study. All study drug doses must be inventoried, accounted for, and returned to NICHD or destroyed per instructions from NICHD and according to local regulations. Detail regarding the tracking and maintenance of study drug supply is provided in the MOP.

5.6 Discussion and Justification of Study Design

The multicenter, randomized, double-masked, placebo-controlled, parallel-group design chosen for this study is generally acknowledged as the “gold standard” for obtaining unbiased estimates of treatment differences.

The study population chosen for evaluation in this study consists of extremely premature infants (<28 weeks’ gestation) who are at high risk for developing ROP. As the incidence of any ROP is inversely proportional to gestation, randomization has been stratified by 2 gestational age strata (<26 and 26-27 weeks), to ensure balance between the treatment groups.

The measurements to be performed in this study are standard for the care and outcome assessment for premature infants. The age of 55 weeks PMA selected for the latest date of evaluation of the primary ROP endpoint was chosen because >99% of acute/favorable outcomes have occurred by this age, and all except rare cases of severe ROP outcomes have developed by this age (Reynolds 2002).

The selection and timing of inositol dosing chosen for this trial was based on published studies as well as the NICHD-sponsored Phase 2, pharmacokinetic, dose-ranging study. Inositol administered at 80 mg/kg/day was the effective dose in the second and larger Hallman trial (Hallman 1992), and in the INS-2 pharmacokinetic study, this dose achieved the serum levels of 126-153 mg/L observed in the Hallman studies during the first 2 weeks of dosing. Administering 80 mg inositol/kg/day in divided doses at 12-hour intervals reduces peak serum levels and therefore reduces renal losses. Repeated dosing did not lead to increasing serum levels over 10 weeks.

The decision to continue treatment through 34 weeks PMA was based on the following rationale: a) Prevention: if ROP is going to develop, it normally is manifest by this time, b) Treatment: ROP that is going to be severe usually changes character and accelerates between 30 and 34 weeks PMA so that extending supplements to this point seemed to offer an advantage, c) Effect on serum levels: results from the repeated dosing INS-2 study of doses between 5 and 80 mg/kg/day show that, despite prolonged dosing, serum levels in all dose groups converge towards the placebo group by 6-10 weeks after birth, and d) Practical considerations: continued dosing after discharge (34-40 weeks PMA on average) becomes impractical.

6 ADVERSE EVENTS

Adverse events (AE) are monitored during the study to ensure timely detection of events that may affect the safety or continued participation of research subjects. In INS-3, this extremely high-risk and fragile population will each experience both expected and unexpected adverse events. Adverse events and their relationship to study, severity, time of experience, expectation, actions taken to resolve the event and final outcome will be recorded as documented in the medical record, or if reported by the NICU team even before documentation.

All adverse events will be followed to conclusion or recorded as ongoing if there will be no resolution. These adverse event rates will be part of reporting the final results of the study, and for the safety monitoring performed by the Data Safety and Monitoring Committee (DSMC).

6.1 Definitions

6.1.1 Adverse Event

An AE is defined as any untoward medical occurrence in a research subject temporally associated with the use of a drug in humans, whether or not considered drug related. Such an event can result from use of the drug as stipulated in the protocol or labeling, as well as from accidental overdose. Any worsening of a pre-existing condition or illness is considered an adverse event. Laboratory abnormalities and changes in vital signs are considered to be adverse events only if they meet protocol-specific criteria. These criteria are described in the Neonatal Toxicity Table and instructions for its use in the MOP.

6.1.2 Serious Adverse Event

If an AE meets any of the following criteria, it is to be reported to NICHD, the Data Coordinating Center of RTI, and the local IRB (per Center-specific IRB procedures) as a serious adverse event (SAE) within 24 hours of the Center being made aware of the event. See section 6.4 for these important reporting requirements.

(Note: Based on the premature infant population studied, the serious adverse event categories of events that result in congenital anomaly/birth defect or require intervention to prevent permanent impairment or damage (devices), or require hospitalization, do not apply when defining events for these infants, and are not listed.)

Death of Subject	An event that results in the death of a subject.
Life-Threatening	An event that, in the opinion of the Investigator, would have resulted in immediate fatality if medical intervention had not been taken. This does not include an event that would have been fatal if it had occurred in a more severe form.
Prolongation of Hospitalization	An event that prolongs the subject's hospital stay.
Results in persistent or significant disability/incapacity	An adverse event that results in a substantial disruption of the ability to conduct normal life functions, i.e., the adverse event resulted in a significant, persistent or permanent change, impairment, damage or disruption in the infants body function/structure, physical activities and/or quality of life.

Important Medical Event Requiring Medical or Surgical Intervention to Prevent Serious Outcome	An important medical event that may not be immediately life-threatening or result in death or hospitalization, but based on medical judgment may jeopardize the subject and may require medical or surgical intervention to prevent any of the outcomes listed above (i.e., death of subject, life-threatening, prolongation of hospitalization). An example of such events would be an allergic bronchospasm requiring intensive treatment.
---	--

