5.3 Efficacy and Safety Assessments/Variables

5.3.1 Specific Treatment Plan and Subject Management

Assessments of efficacy and safety performed during the study and during follow-up are presented in Table 7, Study Activities.

Table 7. Study Activities

Procedures	12-72 ^a hours after birth	Study Day	1	2-35	36-70	71-105	106-140	141-175	176-210	22-26 months corrected
		Study Week		1-5	6-10	11-15	16-20	21-25	26-30	
Informed Consent	X									
Randomization ^a	X									
Cranial Ultrasound ^b				X	X					
Study Drug Administration ^c			X	X	X					
Ophthalmologic Examination ^d				(X)	X	X	X	(X)	(X)	
Infant Growth ^e				X	X	X	X	(X)	(X)	X
Concurrent Medications ^f	X		X	X	X	X				
Adverse Event Assessments ^g	X		X	X	X	X				
Clinical Diagnoses ^h	X		X	X	X	X	X	X	X	X
Follow-up Evaluation ⁱ										X

^a With allowance for up to 72 hours; however, the goal is to enroll as soon a practicable after 12 hours

^b Cranial ultrasounds will be performed at times consistent with clinical practice to evaluate for IVH and PVL. Otherwise they will not be mandated by the study

^c Daily study drug administration will begin following consent and end at 34 completed weeks PMA, 10 weeks chronologic age, or at the time of discharge, whichever occurs first.

^d Ophthalmologic examinations will begin at Week 31 PMA and continue every 1 to 3 weeks based on findings until Acute/Final ROP status is achieved.

^e Weight is recorded weekly, head circumference is recorded every 2 weeks, and length is recorded every 4 weeks.

^f Recorded from 24 hours prior to randomization until discharge, transfer, or 7 days after the last dose of study drug administration, whichever occurs first.

^g Recorded from treatment initiation until 7 days after last dose of study drug

^h Clinical diagnoses will be collected from the medical record throughout hospitalization and again at the follow-up visit.

ⁱ Follow-up evaluations and interval medical data will be collected at 22-26 months corrected age per the NRN Follow-up Protocol (described separately)

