5.5 Treatments

5.5.1 Treatments Administered

Within 12-72 hours of birth, all eligible subjects will begin treatment with 80 mg inositol/kg/day or placebo, according to individual randomization. Study drug will be administered daily and continue until the earliest of 34 weeks PMA, 10 weeks chronologic age, or the time of discharge. Study medication will be administered IV until enteral feeds reach 120ml/kg/day (or sooner if

the infant is no longer receiving IV fluids), at which time the same dose and formulation will be administered enterally.

Inositol: myo-Inositol 5% Injection is an isotonic, preservative-free, sterile 5% solution of myo-inositol in water containing 0.5 gm sodium chloride per liter (8.55mM), pH 6.5-7.5. It is administered via IV infusion using syringe pump over 15-30 minutes twice per day at 12-hour intervals at a dose of 80 mg inositol/kg/day (40 mg inositol/kg/dose), which is equivalent to 1.6 mL/kg/day (0.80 mL/kg/dose).

Placebo: 5% dextrose (5% glucose) in sterile water (D5W pyrogen and preservative free) United States Pharmacopoeia (USP) for IV infusion. Placebo will be administered in the same dose (80 mg glucose/kg/day divided in 2 doses administered every 12 hours) and dispensed in the same manner as the inositol.

Study drug should be infused into a vein rather than an artery because safety for arterial infusion has not yet been tested. It can always be given with a small saline flush preceding and following its infusion into a vein while other infusions are held during the study drug infusion.

Administration through the port of a multi-lumen line is acceptable since there is no mixing of solutions until it reaches the blood stream. In addition, in vitro testing was conducted with commonly used continuous drug infusions (for this population) including various TPN solutions and the results show inositol to be physically compatible with these selected solutions. The study drug may be co-infused with these solutions. See the Investigator's Brochure for specific testing completed and a listing of compatible co-infusion solutions.

Conversion to Enteral Administration

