6.3 Adverse Event Collection Period

All adverse events reported will be collected from the time of first study drug administration until 7 days following discontinuation of study drug. In addition, if an existing condition was present before study drug was started, but became substantially worse afterwards, it will also be reported as an adverse event. Serious adverse events and those events requiring IND safety reporting will be followed until resolution or determination that no resolution is possible.

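### Section 6.1.2 drops hospitalization as a seriousness criterion without limit, although adverse event collection can continue for up to 7 days after discharge home

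*Protocol*

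**What the plan says.** All references are to the protocol.

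- **Seriousness definition (Section 6.1.2).** The opening note begins "Based on the premature infant population studied, the serious adverse event categories of events that result in congenital anomaly/birth defect" and later continues "or require hospitalization, do not apply when defining events for these infants". The criteria that remain are death, immediate threat to life in the investigator's opinion, a lengthened hospital stay, persistent or significant disability, and an important medical event identified by medical judgment. An event that meets one of them goes to the sponsor, the data coordinating center and the local IRB within 24 hours.
- **Collection period (Section 6.3).** "All adverse events reported will be collected from the time of first study drug administration until 7 days following discontinuation of study drug".
- **Table 7 (Section 5.3.1).** Footnote g, on adverse events, reads "Recorded from treatment initiation until 7 days after last dose of study drug". Footnote f, on concurrent medications, reads "Recorded from 24 hours prior to randomization until discharge, transfer, or 7 days after the last dose of study drug administration, whichever occurs first".
- **End of dosing (Section 5.5.1).** Study drug is to "continue until the earliest of 34 weeks PMA, 10 weeks chronologic age, or the time of discharge". Section 5.5.4 confirms that discharge home stops the drug.
- **Discharge age (Section 5.6).** Discharge is put at 34 to 40 weeks PMA on average.

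**The concern.** Dropping hospitalization as a criterion makes sense for infants who are already inpatients, because being in hospital then says nothing about an event. The only reason the note gives is the population, and that reason stops applying once the infant has gone home. From then on a new admission is the usual outward sign that an event was serious.

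What is at stake is classification. The 24-hour report (Sections 6.1.2 and 6.4), the sponsor's decision on expedited reporting (Section 6.1.3) and the serious event rates shown to the DSMC (Section 8.1.1) all start from an event being classed as serious. With approximately 44 sites and no fixed rule for readmission, the same admission could be an SAE at one site and a non-serious adverse event at another. Safety is one of the two primary objectives in Section 4, so the definition should cover the whole period over which events are collected.

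**Working it through.** The protocol states no figure on this point. The check sets the sections side by side, with a little arithmetic on timing.

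**1. Is the exclusion limited in time?** No. The note in Section 6.1.2 gives the population as its reason and makes no exception after discharge.

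**2. Does adverse event collection stop at discharge?** No. Section 6.3 and footnote g end it 7 days after the last dose. Footnote f, directly above, does cut off concurrent medications at discharge or transfer, so the protocol states that limit where it wants it. In the synopsis and Section 5.1 the phrase about discharge or transfer follows the medication clause. It could loosely be read as covering adverse events as well, but Section 6.3 and the contrast between f and g settle the matter.

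**3. When can the window fall at home?** The inputs are the dosing limits in Sections 5.5.1 and 5.5.4 and the 7 days in Section 6.3.

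Latest end of dosing (weeks PMA) = min(34, GA at birth + 10). The window closes one week later.

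| GA at birth | Latest end of dosing | Window closes |
|---|---|---|
| 23 0/7 | min(34, 33) = 33 | 34 |
| 24 0/7 | min(34, 34) = 34 | 35 |
| 27 6/7 | min(34, 37 6/7) = 34 | 35 |

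Let d be the days from last dose to discharge home. Days of the window spent at home = max(0, 7 − d):

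- d = 0 (dosing ended by discharge): 7 days
- d = 1 to 6: 6 down to 1 days
- d of 7 or more: 0 days

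The gap therefore concerns only infants home by about 35 weeks PMA. That overlaps the lower end of the discharge range in Section 5.6.

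**4. Does any remaining criterion make a readmission serious in itself?** No.

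- Death, threat to life and disability depend on the event, not on the admission.
- Prolongation needs a current stay, and an infant at home has none.
- The important-medical-event row depends on medical judgment. The outcomes it aims to prevent are given as death, threat to life and prolongation, without new admission. The same row also speaks of hospitalization as though it were still a listed outcome, so Section 6.1.2 is not quite consistent within itself.

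**5. Can the size be computed?** Expected missed SAEs = N × P(home during the window) × P(readmitted in that time) × P(no remaining criterion met). The protocol gives N, approximately 1760 infants. It gives none of the three probabilities, so no count can be derived.

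**The case against.** The case against giving this much weight is good, and most of it stands.

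- **Other criteria still apply.** A reader might infer that a readmission is an SAE only if somebody chooses to call it important. The text does not support that: fatal, life-threatening and disabling events qualify regardless, and the important-medical-event wording is broad enough to cover many reasons for readmitting such an infant. Judgment is also built into the life-threatening criterion. The gap is the readmission that meets none of these.
- **Events are not lost.** They are still recorded with severity, relatedness and expectedness unless mild and expected (Section 6.2.1). The DSMC reviews rates of all adverse events, not only serious ones (Section 8.1.1). What can be lost is the serious label and the 24-hour report.
- **The window is narrow.** Most infants are probably still inpatients at 35 weeks PMA, and those transferred to another hospital have not gone home.
- **A number is tempting.** A reader might apply a guessed percentage to 1760. That would count infants exposed to the gap, not missed SAEs, and the protocol offers no basis for the percentage.
- **Pharmacology gives little support for urgency.** By 6 weeks into treatment in INS-2, serum levels were similar in the placebo and dose groups (Section 3.3.2.2).
- **The MOP is not at hand.** Section 5.3.3 refers to it for detail on safety variables, and it may address readmission.

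Two points survive. The stated rule in Section 6.1.2 is unlimited, and an MOP that said otherwise would contradict it. Rehospitalizations collected at 22 to 26 months (Section 5.3.3.2) come largely from parental recall and do not replace prompt reporting.

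**Conclusion.** The point holds as a limited gap in the safety definitions. Section 6.1.2 is written for inpatients, while Section 6.3 continues past discharge for infants who go home at the last dose or within 7 days of it. In that time a readmission meeting no other criterion is handled as a non-serious adverse event.

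The affected group is probably a small minority, which is an inference from the 34 to 40 week discharge range rather than a computed share. The number of missed SAEs would be smaller still and cannot be derived. The exclusion applies to both arms alike, and it has no bearing on the primary outcome, sample size, power or type I error. The conclusion rests on reading Section 6.3 and footnote g as written, that is, without a cut-off at discharge. The change is still worth making, because it is cheap and removes a source of inconsistent classification between sites.

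**What to change.** Reconcile Section 6.1.2 with Section 6.3:

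1. Limit the exclusion of the hospitalization category to the initial birth hospitalization, and say that this includes direct transfer from one hospital to another.
2. State that an adverse event leading to readmission after discharge home, within the collection window of Section 6.3, is an SAE reported by the existing 24-hour route.
3. Bring the list of outcomes in the important-medical-event row into line, and carry the wording into the MOP.

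The cost is about one sentence in the protocol, a matching edit in the MOP and a few additional SAE forms. No dosing, assessment or analysis changes.
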